Recruitment is planned to last 1 year and each participant is being followed for 1 year. To assess recruitment yields according to different targets, we stratify on ACEI/ARB and baseline ω-3 use. The first stratum (people not using ω-3) is randomized to placebo or ω-3. The second stratum (people not using ACEI or ARB) is randomized to placebo or LO. The third stratum (people not using ACEI, ARB, or ω-3) is randomized to placebo, LO, ω-3, or the combination. The original ENRGISE targets, based on the estimated proportions in LIFE are presented in Table 6.1. (We note that during the ENRGISE DSMB’s August 23, 2016 phone call, the DSMB approved the investigators’ request to lift the upper limit on the number recruited into stratum 1. In the text which follows, the original sample sizes remain as we do not know how many we will recruit into each stratum. The randomization weights will remain unchanged.) We expect to have a slight imbalance in the overall numbers within each treatment group of 90, 75, 75, and 60. Oversampling of the control group allows us to better estimate parameters associated with IL-6, walking speed, and major mobility disability in that group; this is important for planning the sample-size of the main trial. Note that anybody eligible for stratum 3 is also eligible for strata 1 and 2. To achieve overall balance between the two single interventions, we focus attention on having equal numbers in strata 1 and 2 but do not worry if either is less than 25% of the total as randomizing additional people in strata 3 provides similar information. If 20% were in each of strata 1 and 2, the overall weights would be 0.28, 0.24, 0.24, and 0.24; if 15%, then 0.26, 0.23, 0.23, and 0.28. Both are close to Table 6.1. and do not markedly reduce power for any comparison.

6.2. Interventions and compliance. .

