We use the "intention to treat" approach assuming participants are grouped according to randomization for all analyses of the intervention effect. The stratified recruitment and randomization allow us to compare mean log(IL-6) between each of the three active groups to placebo using a linear mixed model with both main effects and their interaction, adjusted for baseline log(IL-6) and strata. Time is a repeated factor, and the primary comparison is based on a contrast at 12 months. The covariance structure will be assumed to be unstructured. The primary focus is on marginal comparisons (135 and 165/group) between each active intervention and placebo using one-sided hypothesis tests at the 10% level (we are not looking for definitive evidence, but to rule out small effects). We assume 5% loss to follow-up (LTFU); this is similar to the 5% we achieved in LIFE. Using the root mean squared error from LIFE-P (adjusted for baseline log(IL-6) and treatment) of 0.52, we have 91% power to detect a difference if the difference (on the log scale) is at least 0.1625. This is equivalent to the difference between 4.20 and 3.57 pg/ml (or a 15% difference). We would have 66% power for a 10% difference (4.20 vs. 3.78 pg/ml, 0.1054 on the log scale) and 99% power for a 20% difference (4.20 vs. 3.36 pg/ml, 0.2231 on the log scale). Individual treatment group comparisons (at least 60 vs. 75/group) would have 44% power for a 10% difference, 68% power for a 15% difference, and 87% power for a 20% difference. This achieves the first part of Aim a (i). As sensitivity analyses, we also explore the impact of additional factors (e.g., diet, physical activity, medication use) by adding these factors to the models. Although the mixed model is robust against data missing at random (MAR), multiple imputation will be used in sensitivity analyses.

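### The stated 91% losartan power counts stratum 1 as losartan controls (about 83% once strata are adjusted for), and lifting the stratum 1 cap can lower it further by an amount the plan does not quantify

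*Combined protocol and SAP*

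**What the plan says.** Section 6.1 reports DSMB approval "to lift the upper limit on the number recruited into stratum 1". It continues: "In the text which follows, the original sample sizes remain as we do not know how many we will recruit into each stratum". On allocation: "The randomization weights will remain unchanged". Table 6.1 gives stratum 1 a weight of zero for losartan and for the combination, and the text agrees: "The first stratum (people not using ω-3) is randomized to placebo or ω-3".

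The section still expects a "slight imbalance in the overall numbers within each treatment group of 90, 75, 75, and 60". It tests two other mixes, 20% and 15% in each of strata 1 and 2, and says of them: "Both are close to Table 6.1. and do not markedly reduce power for any comparison". No mix with stratum 1 above 25% is shown.

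Section 6.10.b specifies a linear mixed model adjusted for baseline log(IL-6) and strata, tested one-sided at 10%. For the marginal comparison of 135 vs 165 it states 66%, 91% and 99% power for 10%, 15% and 20% differences. It adds: "Individual treatment group comparisons (at least 60 vs. 75/group) would have 44% power for a 10% difference", with 68% and 87% for 15% and 20%.

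**The concern.** A participant in stratum 1 can only be allocated placebo or ω-3. Once the analysis adjusts for strata, that participant contributes nothing to the losartan contrast. The 135 vs 165 calculation nevertheless treats all 75 stratum 1 participants as losartan controls.

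Lifting the cap adds a second problem. With the total fixed at 300, each stratum 1 participant beyond 75 takes a place from strata 2 and 3, the only strata that inform losartan. The alternative mixes in Section 6.1 move stratum 1 down, whereas removing an upper limit can only let it go up.

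The pilot is meant to help decide whether one or two interventions go forward. If losartan is tested with clearly less power than ω-3, and less than stated, a null losartan result may be given more weight than it deserves.

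**Working it through.** **Inputs.** Section 6.10.b: residual SD 0.52 on log(IL-6), 5% loss, one-sided 10% (z = 1.2816), log differences 0.1054, 0.1625 and 0.2231. Table 6.1: weights for placebo / losartan / ω-3 / combination of 0.4/0/0.6/0 (stratum 1), 0.4/0.6/0/0 (stratum 2) and 0.2/0.2/0.2/0.4 (stratum 3), and LIFE shares of 44.1%, 10.7% and 45.3%. Assumptions: total 300, loss equal across arms, the same SD in every stratum, strata as fixed effects. The 50/10/40 and 60/10/30 mixes are illustrative.

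**1. Reproduce the plan.** Power = Φ(d/SE − 1.2816), with SE = 0.52 × √(1/n₁ + 1/n₂) and group sizes multiplied by 0.95.
- 135 vs 165: SE = 0.52 × √(1/128.25 + 1/156.75) = 0.0619. For 0.1625: Φ(2.625 − 1.282) = 91.0%. The 10% and 20% differences give 66.3% and 99.0%.
- 60 vs 75: 44.4%, 68.3% and 87.1%.

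All six stated figures reproduce.

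**2. Adjust for strata at the planned mix.** In both strata 2 and 3, 60% receive losartan (0.6, and 0.2 + 0.4) and 40% do not. With E = n₂ + n₃, the information is 0.6 × 0.4 × E, so SE = 0.52/√(0.95 × 0.24 × E).
- E = 225: SE = 0.52/√51.3 = 0.0726; power = Φ(2.238 − 1.282) = 83.1%.
- A linear model that also adjusts for ω-3 gives 82.7%.

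So about 8 points of the stated 91% are absent with the cap still in place.

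**3. Let stratum 1 grow, total 300.** At the LIFE shares the strata are 132.3, 32.1 and 135.9. The arms become:
- placebo 0.4 × 132.3 + 0.4 × 32.1 + 0.2 × 135.9 ≈ 93
- losartan alone 0.6 × 32.1 + 0.2 × 135.9 ≈ 46
- ω-3 alone 0.6 × 132.3 + 0.2 × 135.9 ≈ 107
- combination 0.4 × 135.9 ≈ 54

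For losartan E = 168: SE = 0.52/√38.3 = 0.0840; power = Φ(1.934 − 1.282) = 74.3% (73.9% adjusting for ω-3). For ω-3 the informative strata are 1 and 3, so E rises from 225 to 268: SE = 0.0665, power 87.7% (87.4% adjusting for losartan).

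Main-effect power for a 15% IL-6 difference:

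| Strata 1/2/3 (%) | Arms: placebo / losartan / ω-3 / combination | Losartan, plan's unstratified method | Losartan, strata-adjusted | ω-3, strata-adjusted |
|---|---|---|---|---|
| 25/25/50 (planned) | 90 / 75 / 75 / 60 | 91.0% | 83% | 83% |
| 44.1/10.7/45.3 (LIFE) | 93 / 46 / 107 / 54 | 88.7% | 74% | 87% |
| 50/10/40 | 96 / 42 / 114 / 48 | 87.2% | 70% | 88% |
| 60/10/30 | 102 / 36 / 126 / 36 | 83.4% | 64% | 88% |

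**4. Losartan alone vs placebo, within strata.** Information is 0.24 × n₂ (0.6 vs 0.4) plus 0.10 × n₃ (0.2 vs 0.2).
- Planned: 18.0 + 15.0 = 33.0; SE = 0.52/√31.35 = 0.0929; power 68%, the same as the stated figure.
- LIFE mix: 7.7 + 13.6 = 21.3; SE = 0.52/√20.2 = 0.1157; power 55%.

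This fall is a like-for-like effect of the mix. The same comparison for ω-3 alone rises from 68% to about 78%.

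**5. Walking speed, 0.038 m/s.** With SD 0.21 and r = 0.80, the residual SD is 0.21 × √(1 − 0.64) = 0.126. Within strata, losartan power is 81% at the planned mix and 72% at the LIFE mix. The unstratified method gives 89.5% and 86.9%. The stated 86% for 135 vs 165 is not matched exactly at r = 0.80, so only comparisons within one method are used here.

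**The case against.** The change is disclosed. Section 6.1 gives the date and the DSMB approval, and says the original sizes are kept because the final stratum numbers are unknown. The IL-6 power figures follow from their stated inputs. This stands: it is neither an arithmetic error nor a hidden inconsistency.

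A reader might attribute the whole drop from 91% to 74% to lifting the cap. The documents do not support that. About 8 points come from the unstratified calculation and exist at the planned mix; about 9 come from the LIFE mix. By the plan's own method that mix costs about 2 points. For the same reason, 72% for walking speed should not be set against the stated 86% as a cap effect.

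A reader might also infer that every power figure is out of date. That is too broad: the correlation power in Section 6.10.c uses 285 of 300 participants and does not depend on the mix. Nor is the reassurance in Section 6.1 about power wrong, since it refers only to the 20% and 15% mixes.

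The loss depends on an unknown share and on displacement within 300. If stratum 1 recruits were added on top (150/75/150), strata-adjusted losartan power would stay near 83%. The pilot is also not decided by one test: Section 6.10.e weighs yield, safety, tolerability and other evidence, and power for a 20% difference is still about 91% at the LIFE mix. These points limit the consequence. They do not remove the gap between the stated power and the planned analysis.

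**Conclusion.** The point holds in two separate parts, both for a 15% IL-6 difference. Under the planned strata adjustment, losartan main-effect power is about 83% rather than 91%, whatever happens to the cap. If the total stays at 300, growth in stratum 1 lowers it further: about 74% at the LIFE mix and 64% at 60/10/30. Losartan alone vs placebo goes from 68% to 55% at the LIFE mix, and two arms drop below the stated floor of 60. The two drugs, equally powered in the original design, would no longer be so. The aim in Section 6.1 of equal numbers in strata 1 and 2 also sits poorly with an uncapped stratum 1: the LIFE mix would give about 132 and 32.

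The first part needs only the plan's own inputs and strata treated as fixed effects. The size of the second is conditional: LIFE is a scenario from another trial, not a forecast, and the other mixes are illustrative. Disclosing that the mix is unknown is a reason to show a range above 25%, which the plan does not do.

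**What to change.** - State whether the total stays at 300 now that stratum 1 has no upper limit, or whether extra stratum 1 recruits are added to it.
- Replace the single marginal power figure in Section 6.10.b with a short table of arm sizes and strata-adjusted power, separately for losartan and ω-3 and for both IL-6 and walking speed, at stratum 1 shares of about 25%, 44% and 60%.
- Remove the minimum group sizes for individual comparisons, or state the mix they depend on.

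The cost is one table and a few sentences. The stated losartan power becomes less favourable. Recruitment, allocation and treatment do not change.

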5.	Biological mechanisms are considered to prioritize interventions that target different inflammatory mechanisms or may have synergistic effects. We exclude interventions that may negatively affect skeletal muscle metabolism.
6.	Practical and affordable for implementation in the US health care system. Cost is a major factor for this criterion to maximize the public health impact of the trial

ω -3 reduced IL-6 by >50% in RCTs^{75, 76} and **ARBs reduced IL-6 by >40%**^{77, 78} and by **58%**⁷⁹ in RCTs. In Health ABC¹ and EPESE,² we have found that **a 50% lower IL-6 plasma level was associated with approximately 50% lower risk of mobility disability** over 2.5 and 4 years of follow-up, respectively. Change in IL-6 induced by LO and ω -3 may depend on the target population, baseline IL-6 level, dosage, compliance, and duration of treatment. Thus, the pilot study is of key importance to probe their anti-inflammatory effects in the ENRGISE population.

Inclusion of potential candidate interventions (see Table 5.2.)

Angiotensin Converting Enzyme Inhibitors (ACEIs) and ARBs have shown excellent safety in large hypertension and heart failure trials in older persons,⁸⁰⁻⁸⁴ Among ACEIs, perindopril^{85, 86} and enalapril⁶⁵ have demonstrated reductions in IL-6. Perindopril has shown to prevent physical function and walking speed decline in older persons,⁸⁷ to reduce CRP,⁸⁸ and to have a favorable safety profile.⁸⁹ Dual angiotensin blockade with ACEIs and ARB results in higher risk of adverse events,⁹⁰ thus, we do not recommend to combine ACEIs and ARBs. Virtually all ARBs, except azilsartan, have been shown to reduce elevated IL-6.^{65, 77, 91-102} Telmisartan improved walking distance in patients with peripheral artery disease¹⁰³ and running endurance in mice.¹⁵ In older mice LO reduced IL-6 and improved physical performance.⁶⁶ We prioritize ARBs because of greater tolerability than ACEIs,^{83, 84, 104} and among ARBs, we prioritize LO due to its low cost (1/50 that of other ARBs). Among nutritionals, ω -3⁶² and lipoic acid^{92, 105} reduce IL-6^{62, 92, 105} and CRP^{62, 106} in RCTs. The evidence of the

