additional biomarkers, their relationship with walking speed and their impact on recruitment and effect size estimates; and (10) estimate the cost of the main trial.

Table 6.1. Randomization strata according to medication use at baseline – Total N=300

Strata according to medication use at baseline	LIFE N (%) Observed	ENRGISE pilot N (%) Proposed	Randomization weights			
			Placebo LO Placebo ω-3	LO Placebo ω-3	Placebo LO ω-3	LO ω-3
1 No ω-3 (ACEI/ARB ok)	637 (44.1)	75 (25%)	0.4*	0	0.6*	0
2 No ACEI/ARB (ω-3 ok)	154 (10.7)	75 (25%)	0.4**	0.6**	0	0
3 No ACEI/ARB, No ω-3	655 (45.3)	150 (50%)	0.2	0.2	0.2	0.4
Overall		300 (100%)	0.3 (n=90)	0.25 (75)	0.25 (75)	0.2 (60)

* Does not receive placebo LO, and ** does not receive placebo ω-3 as the use of the corresponding drugs is permitted at baseline

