- The participant is diabetic and fasting glucose > 300 ,
- Baseline LDL > 130 AND increases by $\geq 20\%$ from baseline,
- The participant is taking a blood pressure lowering agent OR is also participating in the Losartan arm of the study AND blood pressure is $<90/50$, or
- Participant does not tolerate the fish oil.

The principal investigator/study physician at each site has the discretion to opt out of ω -3 fish oil dose adjustments due to glucose and/or LDL levels.

We increase the dose of ω -3 fish oil to 2.8 g/day if the average of IL-6 measured at 3- and 6-month visits has not **decreased by at least 40%** vs. baseline (average of screening visits 1 and 2). The 40% threshold is selected based on previous trials with ω -3 fatty acids. ω -3 fatty acids have been shown to reduce IL-6 by $>50\%$ in RCTs^{75, 76} and to be consistent with the threshold used below for losartan. To minimize the impact of outliers due to acute illness, the 3-month or the 6-month IL-6 measure are excluded or postponed if there is an acute illness within one month prior to the visit. In the rationale for dose titration we use the following assumptions:

1. IL-6 biovariation as a CV is $\sim 30\%$. This is a reasonable estimate based on our own estimates (unpublished data) and those of others.^{150, 151} This means that a SD of each person's day to day variability is about 30% of the mean value.
2. We have two measures at baseline that can be averaged to yield a reasonable estimate of each person's average value.
3. For dose adjustment we use IL-6 measured at 3 months and 6 months.
4. The half-life of IL-6 is extremely short (<30 minutes), so response to interventions is essentially coincident to the effect of the interventions.
5. We screen for outliers by excluding participants who experienced an acute illness within a month of the visit

6.2.b. LO and placebo (cellulose based) are obtained in 25 mg and 50 mg capsules. The shell capsules are cellulose based. Placebo and LO have identical shape, color, taste and weight. We start with 25 mg/day, if tolerated, we step up to 50 mg/day. If there are no safety concerns, we continue with 50 mg/day until the 6 month visit. If the average of IL-6 measured at 3- and 6-month visits does not **decrease by $\geq 40\%$** vs. baseline (average of screening visits 1 and 2), we increase the dose to 100 mg/day. Equivalent doses of ARBs have shown to reduce IL-6 by $>40\%$ ^{77, 78} and by 58% ⁷⁹ in RCTs.

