6.3. Safety dose titration. ARBs produce blood pressure reductions similar to those seen with ACE inhibitors and other antihypertensive classes. These drugs vary in efficacy and duration of action but all are recommended for once daily dosing. Like ACE inhibitors, duration of antihypertensive effects is dose-dependent; therefore, smooth blood pressure control over 24 hours is most likely at the maximum recommended dose. To avoid precipitous initial fall in blood pressure or decline in renal function, we start therapy with the lower dose of losartan (25 mg/day). If there are no safety concerns, the dose is increased to 50 mg/day and safety is again checked in about 1 week. To identify abrupt reduction in renal function that warrants drug dose reduction and to avoid dangerous hyperkalemia, we measure eGFR, potassium, and blood pressure before and soon (approximately 1 week) after starting losartan and after any dose adjustment. However, dose adjustments downward that are not related to renal function or hyperkalemia will not require a short-term follow-up blood draw.

In general, losartan dose will be maintained if ALL of the following criteria are met:

- Blood pressure is $\geq 100/50$ and $< 110/50$,
- Potassium < 5.5 ,
- eGFR has NOT declined by $\geq 20\%$ from baseline, and
- No symptoms of lightheadedness or dizziness.

Losartan dose will be decreased if ALL of the following criteria are met:

- Blood pressure is $\geq 90/50$ and $< 100/50$,
- Potassium < 5.5 ,
- eGFR has NOT declined by $\geq 20\%$ from baseline, and
- No symptoms of lightheadedness or dizziness.

Losartan dose will be stopped if ANY of the following criteria are met:

- Blood pressure $< 90/50$,
- Potassium ≥ 5.5 ,
- eGFR decline $\geq 20\%$ from baseline, or
- Symptoms of dizziness, lightheadedness, or syncope.

The principal investigator/study physician at each site has discretion to alter the losartan titration schedule on a case by case basis.

We increase the dose of losartan to 100 mg/day if the average of IL-6 measured at 3- and 6-month visits is not **decreased by at least 40%** vs. baseline (average of screening visits 1 and 2). The 40% threshold

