was selected based on previous trials with ARBs. ARBs have been shown to reduce IL-6 by >40%^{77, 78} and by 58%⁷⁹ in RCTs, and to be consistent with the threshold used above for ω -3 fish oil. To minimize the impact of outliers due to acute illness, the 3-month or the 6-month IL-6 measure are excluded or postponed if there is acute illness within one month prior to the visit.

As part of the safety monitoring of the ENRGISE interventions, we measure blood pressure, blood hemoglobin, serum glucose, eGFR, LDL cholesterol, and potassium at baseline and at 3, 6, and 9 months of follow-up. In addition for those in the losartan arm of the trial, blood pressure, serum potassium, and eGFR, are measured about 1 week after randomization and about 1 week after any losartan dosage adjustment. However, serum potassium and eGFR are not measured one week after a downward dose adjustment that was not based on potassium or eGFR values.

6.4. The Investigational New Drug (IND) Per requirement of the Institutional Review Board, #IND124103 was submitted and approved by the FDA with the mention “STUDY MAY PROCEED”

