6.6. Recruitment – inclusion/ exclusion criteria - (details in Table 6.2.)

We identify men and women aged ≥ 70 years who are **able to complete the 400 m walk** at baseline, and are at **high risk of mobility disability** assessed by

- Self-reported difficulty walking ¼ mile or climbing a flight of stairs,
- Usual walking speed <1 m/sec and >0.44 m/sec on the 4 m walk (in the pilot phase we explore the feasibility of recruiting at least 50% of participants who have a baseline walking speed of <0.80 m/sec and >0.44 m/sec),^{22, 154, 155} and
- Chronic low-grade inflammation measured by IL-6 >2.5 pg/ml, the threshold we have found for increased risk of mobility limitation,^{1, 2} and <30 pg/ml to exclude high grade inflammation. To minimize within person variability,^{150, 156} IL-6 is the average of 2 measures taken at screening visits, with the first measure being >2.3 and <30 pg/ml, and the average of the two measures >2.5 and <30 pg/ml.

We exclude subjects with acute, autoimmune and HIV illnesses and causes of low walking speed that may be related to neurological conditions, severe arthritis, or low vitamin D. Other exclusion criteria reflect conditions that may interfere with the conduct of the study, interventions or assessments. Those taking ACEI or ARB are excluded from the LO randomization and those eating >2 servings/week of fish in the past year or taking fish oil are excluded from the ω -3 randomization. We recruit from the community. We use recruitment strategies successfully applied in LIFE,¹⁵⁷ LIFE-Pilot,¹⁵⁸ and TTrial,¹⁵⁹ which include primarily mass mailing, and newspaper, radio and TV ads and explore alternative recruitment strategies, such as electronic medical records to identify patients not taking study drugs and assess whether that strategy is effective in lieu of or in addition to mass mailing.

Table 6.2. Inclusion and exclusion criteria

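### ACEI/ARB use bars entry to losartan, but no rule requires action when one is started after randomisation, and the month-6 rise to 100 mg/day is not guarded against it

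*Combined protocol and SAP*

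**What the plan says.** **At entry.** Section 5 (Background, on candidate interventions) notes more adverse events with dual angiotensin blockade and concludes: "thus, we do not recommend to combine ACEIs and ARBs". Section 6.6 applies this: "Those taking ACEI or ARB are excluded from the LO randomization". Table 6.2 adds a 2-month look-back for both classes. The Table 6.1 footnote explains that people in stratum 1 receive no losartan-type capsule, "as the use of the corresponding drugs is permitted at baseline". The issue therefore concerns strata 2 and 3 only.

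**During follow-up.** Section 6.3 has maintain, decrease and stop lists. The last opens "Losartan dose will be stopped if ANY of the following criteria are met" and gives four triggers: blood pressure below 90/50, potassium of 5.5 or more, an eGFR decline of at least 20%, or dizziness, lightheadedness or syncope. Scheduled safety bloods are taken "at baseline and at 3, 6, and 9 months of follow-up". Blood pressure, potassium and eGFR are also checked about 1 week after randomisation and after losartan dose changes, but no draw follows a reduction made for other reasons.

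**Dose rise.** Section 6.2.b says that if mean IL-6 at months 3 and 6 has not fallen by at least 40% from baseline, "we increase the dose to 100 mg/day". Section 6.3 repeats it: "We increase the dose of losartan to 100 mg/day if the average of IL-6 measured at 3- and 6-month visits" misses that threshold. Neither sentence has a co-medication condition. The site physician "has discretion to alter the losartan titration schedule on a case by case basis".

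**The concern.** The protocol takes a position on a drug combination, enforces it at randomisation, and then gives no instruction if the combination arises later. It does handle co-medication elsewhere: one omega-3 adjustment criterion in 6.2.a.1 depends on taking a blood-pressure-lowering agent, and 6.2.b.1 discusses NSAIDs with losartan and points to renal monitoring.

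A later start is foreseeable. Participants are 70 or older, hypertension excludes only when severe (for example systolic above 200 or diastolic above 110), and blood pressure alert values go to participants' own physicians. Treatment is double-blind, so a prescriber need not know that losartan is being taken. Entry to losartan is barred for renal function only at eGFR below 15, while 6.2.b.1 describes hyperkalemia as rare except in renal impairment.

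At stake is participant safety. Someone whose readings stay within the limits could remain on losartan plus an ACEI or a second ARB, and at month 6 could have the dose doubled from 50 to 100 mg/day, without any rule requiring the combination to be considered.

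**Working it through.** The plan states no figure on this point, so there is none to reproduce except the IL-6 power, which is used to cost the fix.

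**1. Text check.**
- Stop, decrease and maintain lists (6.3): no co-medication item.
- Event-driven potassium/eGFR checks (6.3): triggered by randomisation and losartan dose changes, not by a new drug.
- 100 mg/day sentences (6.2.b, 6.3): conditioned on IL-6, with no exclusion for ACEI/ARB users.
- Table 6.3: safety bloods at months 3, 6 and 9, with none marked at the 12-month visit, although capsules are dispensed at month 9. The wait for scheduled bloods is therefore up to about 3 months, and after month 9 none is scheduled unless the dose changes.

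**2. People exposed (Table 6.1).**
- Capsule takers: 75 + 150 = 225.
- Active losartan: 0.6 × 75 + (0.2 + 0.4) × 150 = 135.
- Placebo-losartan: 225 − 135 = 90.

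The rate of new ACEI/ARB starts is not in the documents. Assume 1% to 10% per year, spread evenly:
- Active-losartan starters: 1.35 to 13.5.
- Before month 6 (half): 0.7 to 6.8.
- After month 9 (a quarter): 0.3 to 3.4.

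Section 6.1 lifts the cap on stratum 1. If that stratum became half of the 300, active losartan would be 0.6 × 150 = 90, with 0.9 to 9 starters.

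**3. Chance of meeting the step-up rule.** P(observed fall < 40%) = Φ[(ln(1 − true fall) − ln 0.6)/SD]. One SD is 0.294: the 30% CV in 6.2.a.1 gives a log SD of √ln(1.09) = 0.294 per value, and the difference between two means of two values has the same SD. The other is 0.52, the LIFE-P root mean squared error in 6.10.b, used as a wider alternative.

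| True IL-6 fall | SD 0.294 | SD 0.52 |
|---|---|---|
| 10% | 91.6% | 78.2% |
| 20% | 83.6% | 71.0% |
| 40% | 50.0% | 50.0% |
| 58% | 11% | 24.6% |

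Active-losartan participants who both start before month 6 and meet the rule:
- 10–20% fall: 0.675 × 0.71 = 0.5 to 6.75 × 0.916 = 6.2.
- 40% fall: 0.3 to 3.4.
- 58% fall: 0.1 to 1.7.

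These are upper figures. They remove nobody already stopped or reduced under 6.3. By the Background's own account an ACEI or ARB may lower IL-6. The general rule to maintain the dose at 100–110 systolic also argues against a rise.

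**4. Power cost of withholding the capsule.** Power = Φ(δ/SE − 1.2816), with SE = 0.52 × √[1/(0.95 n₁) + 1/(0.95 n₂)], one-sided 10%, 5% loss. For 135 vs 165 and δ = 0.1625, SE = 0.0619 and power = 91.0%, which matches 6.10.b. In the worst case 10% start, all are still off the capsule at month 12, and they lose the whole effect: δ = 0.9 × 0.1625 = 0.146.

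| Comparison | Full effect | Worst case |
|---|---|---|
| 135 vs 165 (protocol's basis) | 91% | 86% |
| 135 vs 90 (capsule strata only) | 83% | 77% |
| 90 vs 210 (stratum 1 half of 300) | 87% | 81% |
| 90 vs 60 (same, capsule strata only) | 71% | 64% |

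**The case against.** The strongest reply is that existing safeguards already cover most of the risk.

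- Staying on 50 mg/day until month 6 is conditional on there being no safety concerns (6.2.b). Given the Background statement, a known ACEI start is naturally such a concern.
- Section 7.4 has the study nurse or medical safety officer reviewing medication use, and Table 6.3 has a medical history update at every follow-up visit.
- Anyone raised to 100 mg/day has blood pressure, potassium and eGFR measured at month 6 and again about 1 week later. The stop limits target the hypotensive, renal and potassium effects expected from dual blockade, whatever their cause.
- Site discretion, Extra visits and the Intervention and Safety Committee allow action at any time.

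All of this stands. A reader might infer that the protocol obliges sites to continue dual blockade unmonitored; it does not. What the safeguards lack is a required action. The no-safety-concerns condition does not name co-medication and is not repeated for the 100 mg step. The medication review has no consequence attached. Discretion could be used differently across five field centers.

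Two further limits also stand. The Background advice literally concerns an ACEI with an ARB. It does not discuss a second ARB on top of losartan, although Table 6.2 bars both classes at entry. And the counts above are exposures, not harms: the documents give no excess event rate.

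**Conclusion.** The gap is real and limited. No rule requires action on an ACEI or ARB started after randomisation. The uncovered part is the wait of up to about 3 months for scheduled bloods, the period after month 9, and the 100 mg step. The number affected is unknown. About 1 to 14 of 135 on active losartan rests on an assumed start rate of 1–10% per year and on Table 6.1 sizes, and it falls to about 1 to 9 of 90 if stratum 1 becomes half of the sample.

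A reader might also infer that the losartan IL-6 contrast is materially biased. The documents do not support that: they give no start rate, and nothing shows that starts would be numerous or differ between arms. The consent form and any operations manual were not available and might address the point. On the text supplied, this is a minor-to-moderate safety improvement.

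**What to change.** 1. In the 100 mg/day sentences of 6.2.b and 6.3, add: *and the participant is not taking an ACEI or ARB*.
2. In 6.3, after the stop criteria, add: *If a participant in stratum 2 or 3 starts an ACEI or ARB after randomisation, the losartan or placebo-losartan capsule is withheld, without unblinding, while that drug is taken. Blood pressure, potassium and eGFR are measured at an Extra visit within about 1 week of the site learning of it. Any restart is at 25 mg/day with the usual 1-week check, once the study physician confirms eligibility under Table 6.2.* State this as an exception to the two sentences in 6.3 that waive the blood draw after a downward adjustment not based on potassium or eGFR; otherwise the texts conflict.
3. Keep these participants in the intention-to-treat analysis.

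The cost is one paragraph, one clause in two sentences, and one Extra visit per starter: 225 × 1% to 225 × 10%, or about 2 to 23 capsule takers at Table 6.1 sizes. The main downside is that, for a long-term prescription, withholding is in effect discontinuation, including for people on placebo. The worst-case power loss is 5 to 7 percentage points across the four comparisons above; the 86% and 77% figures are not floors if stratum 1 grows.
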